10.2 Statistical and Analytical Plan for Pharmacokinetic Evaluation

For the sparse sampling, descriptive statistics (mean, median, min, max, standard deviation and % coefficient of variation (CV)) will be calculated per sampling day and sample collection interval. A separate Data Analysis Plan (DAP) will be prepared prior to the population PK analysis.

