7.2 Treatment and Dosing Regimen for Study Drug

The study drug will be administered as adjunctive treatment at specific times relative to the PE procedures. The study drug consists of 10 mg of ALX-0081 or placebo, once or twice daily as explained below (Table 8).

Subjects will receive a first i.v. bolus of 10 mg ALX-0081 or placebo via push injection within 6h, but not later than 15 min prior to the initiation of PE on study (i.e., the very first PE session, if the subject was randomised prior to the initiation of PE, or the second PE session, if the subject was randomised after one, single PE session; see section 4.2). This first PE on study is followed by s.c. administration of 10 mg study drug within 30 minutes after the end of the PE procedure.

During the complete PE treatment period (including tapering and PE given for exacerbations), study drug will be administered daily via s.c. injections.

- If 1 PE per day is scheduled, 10 mg of study drug will be administered within 30 minutes after the end of the PE procedure.
- If 2 PEs per day are scheduled, 10 mg of study drug will be administered within 30 minutes after the end of each PE procedure. The maximum total daily dose of study drug is hence 20 mg.
- If less than 1 PE per day is scheduled (i.e. during a tapering regimen), 10 mg of study drug will be administered daily. On days with a PE, study drug administration should be within 30 minutes after the end of the PE procedure; on days without PE, study drug administration should be 24 h (\pm 1 h) after previous administration

Daily s.c. study drug administration of 10 mg will continue for 30 days after the very last PE (including tapering).

Maximum treatment duration with study drug will be limited to 90 days after first administration of study drug.

In case of exacerbation of TTP (after \geq 1 day but \leq 30 days after the last daily PE), standard treatment (PE) should be re-initiated and daily s.c. administration of study drug continued.^a The “study drug post-PE” period (for 30 days after the very last PE, see Figure 5 further below) will re-commence once PE is again stopped. Maximum treatment duration with study drug will be limited to 90 days after first administration of study drug.

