- Blood sampling for coagulation variables will include: fibrinogen, aPTT, PT, INR, vWF Ag and FVIII chromogene (local laboratory). In case FVIII chromogene is not available in the local laboratory, it can be replaced by an alternative method (e.g. one stage clotting assay). The blood samples will be drawn on Mondays, Wednesdays,

and Fridays during daily PE period, on the first day after the daily PE period and then weekly until the last day of study drug administration.

- Blood sampling for markers for cardiac cell death: Troponin T (local laboratory). Daily during daily PE period, on the first day after the daily PE period and then weekly until the last day of study drug administration. In case the two initial measurements indicate that values are < ULN, all subsequent tests can be omitted. In case Troponin T is not available in the local laboratory, it can be replaced by Troponin I.
- Blood sampling for markers for heart failure: BNP or NT-proBNP (local laboratory). The blood samples will be drawn on Mondays, Wednesdays, and Fridays during daily PE period, on the first day after the daily PE period and then weekly until the last day of study drug administration. In case the two initial measurements indicate that values are <ULN, all subsequent tests can be omitted.

Sampling for central laboratory:

- Blood sampling for markers for brain damage: NSE, S β 100 (central laboratory). The blood samples will be drawn Mondays, Wednesdays, and Fridays during daily PE period, on the first day after the daily PE period and then weekly until the last day of study drug administration.
- Blood sampling for RICO (central laboratory). Daily during daily PE period (pre-PE), on the first day after the daily PE period and then weekly until the last day of study drug administration.
- Blood sampling for PK, vWF and FVIII assessments (all central laboratory) need to be taken at the following time points or time intervals:
 - During daily PE period:
 - 3 samples on day 1: at 5-10 min, 3-6 h, and 8-24 h post- i.v. administration of study drug, but prior to the second PE
 - 4 samples on day 2: after PE, but prior to s.c. study drug, and at 1-6 h, 6-12 h, and 18-24 h post-study drug, but prior to the next PE
 - 1 sample on last day of PE: after PE, but prior to s.c. study drug
 - On first day after the daily PE period:

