 - 4 samples: prior to study drug and at 1-6 h, 6-12 h, 18-24 h post-study drug, but prior to next administration of study drug or before next PE (in case of tapering)
 - Subsequent time interval until the last day of study drug administration:
 - 2 samples once-weekly: prior to study drug administration (but after PE, in case of tapering) and 4-8 h post-study drug. Of note, for each day that a follow-up at the investigational site is planned, the

administration of 10 mg study drug will be performed during the follow-up visit in the investigational site.

- Blood samples for ADA (central lab) need to be taken on day 14, and then weekly until the last day of study drug administration.
- Blood sampling for ADAMTS13 and anti-ADAMTS13 antibody titre (central laboratory). This blood sampling needs to be performed on the first day after the daily PE period and 1 week post last day of PE (including tapering) and at 3 weeks post last day of PE (including tapering); the 1 week and 3 weeks after the very last PE (including tapering) sampling may be done at the weekly visit, even if not exactly 1 or 3 weeks.
- Retrieval of 30 mL from the first bag of pathological spent plasma resulting from the first PE procedure on study. This will be divided in aliquots of 5 mL each for storage at -70°C. The retrieved spent plasma, obtained from the first plasma exchange on study, and the first spent bag will be used for following purposes.
 - As matrix for development and validation of ADA, biomarker assays that will be used in TITAN trial.
 - For further characterisation of possible immunogenicity findings.
 - For additional measurement of vWF and ALX-0081 concentrations under R&D conditions and subsequent PK/PD modelling to assess extent of removal of these components upon plasma exchange.
- Recuperate nurse sheet and/or AE diary at each post discharge visit.

An overview of assessments performed during the treatment phase of this trial is provided in Table 11.

Assessments scheduled in case of TTP exacerbation

In case of TTP exacerbation, defined as recurrent thrombocytopenia following a response and requiring a re-initiation of daily PE treatment after ≥ 1 day but ≤ 30 days after the last daily PE, the assessments scheduled for “Day 1 after last daily PE” are not performed after completion of the exacerbation treatment, instead, the “post-daily PE (including tapering)” assessments are continued. A dedicated schedule of assessments is provided in Table 12.

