8.4.4 Pharmacokinetics

Predose plasma concentrations against time will be plotted to demonstrate attainment of steady state.

A separate PK-report will be written and presented as an Appendix to the final Clinical Study Report.

The plasma concentration-time data of ALX-0081 will be analysed using population PK modeling. Typical population values of basic PK parameters will be estimated together with the inter-individual variability. Effects of subject demographics, laboratory parameter values, and other covariates on the pharmacokinetics of ALX-0081 will be explored. The results of the population PK analysis will be reported in an independent Modeling and Simulation report.

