10.1 Study Populations

Populations for the primary and secondary endpoint analyses

The primary analysis population will be the intent-to-treat (ITT) population, which will consist of all randomised subjects according to the randomised treatment assignment. In addition, for the efficacy analyses, the per protocol population (PP) will be used. The PP population will be a subset of the ITT population and will consist of all randomised subjects, according to the randomised treatment assignment, with exclusion of all major protocol violators.

Population for the safety analysis

The safety population will consist of all subjects who received at least one dose of study drug, with treatment assignment designated according to actual treatment received.

Population for the PK analyses

The PK analyses will be performed on the PK population, which will consist of all subjects who have received study drug and for whom the primary PK data are considered to be sufficient and interpretable.

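### PK summaries and the predose plot ignore plasma-exchange (PE) state, so the predose series changes meaning when daily PE stops and the day-1 3-6 h cell mixes conditions

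*Protocol*

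**What the plan says.** Protocol section 10.2 states that descriptive statistics for the sparse PK samples "will be calculated per sampling day and sample collection interval". SAP section 6.5.1 presents concentration profiles and summary statistics by treatment and overall, in the PK population. Section 8.4.4 adds: "Predose plasma concentrations against time will be plotted to demonstrate attainment of steady state".

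The sampling times are in protocol section 8.1.2:

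- Day 1: "3 samples on day 1: at 5-10 min, 3-6 h, and 8-24 h post- i.v. administration of study drug", all before the second PE.
- Day 2: "after PE, but prior to s.c. study drug, and at 1-6 h, 6-12 h, and 18-24 h post-study drug", the last of these before the next PE.
- Last PE day: one sample, after PE and before the s.c. dose.
- First day after daily PE: one sample before study drug, then three after it.
- Weekly thereafter: "prior to study drug administration (but after PE, in case of tapering) and 4-8 h post-study drug".

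Section 7.2 sets the i.v. bolus "within 6h, but not later than 15 min prior to the initiation of PE on study" and places an s.c. dose within 30 minutes after that PE ends. In section 8.1.2 the retained spent plasma is to support modelling "to assess extent of removal of these components upon plasma exchange".

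On the population, section 10.1 says: "The PK analyses will be performed on the PK population, which will consist of all subjects who have received study drug", provided their primary PK data are sufficient and interpretable. Section 6 counts the matching placebo as a study drug.

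**The concern.** A predose series supports a steady-state claim only if every point is taken under the same conditions. Here, PK samples labelled as before an s.c. dose are taken just after PE while daily PE continues. Once it stops, they are ordinary troughs about a day after the previous dose. If PE removes drug, values will rise at the changeover even when nothing about the drug's kinetics has changed. In the phase I volunteer study, which involved no PE, steady state was reached with the first dose (protocol 2.4.2), so such a rise could easily be misread as accumulation.

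The same omission leaves some table cells without a defined condition, chiefly the day-1 3-6 h interval. Separately, an overall PK column has no meaning if it averages treated and placebo subjects.

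The PK and PD profile is a secondary endpoint (protocol 4.1.2). Its descriptive interpretation is at stake. No hypothesis test or sample-size figure depends on it.

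**Working it through.** The plan gives no figure to reproduce. The check traces each sample to its PE state and then sizes two consequences under stated assumptions.

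**1. PE state of scheduled samples before an s.c. dose (protocol 8.1.2, Table 11)**

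| Sampling day | PE immediately before the sample? |
|---|---|
| Day 2 | Yes |
| Last PE day | Yes |
| First day after daily PE | No |
| Weekly, no tapering | No |
| Weekly, tapering | Yes on PE days, otherwise no |

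A single time axis therefore joins two kinds of value.

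**2. Size of the step when PE stops**

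Assumptions, none of them from the documents: linear kinetics, one unit dose daily, a fraction r of the post-dose level left at 24 h, and PE removing a fraction f just before the predose sample.

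- PE-phase predose plateau: P = r(1 − f) / [1 − r(1 − f)].
- First predose value after PE stops: r(P + 1). Since P = (1 − f) × r(P + 1), its ratio to P is 1/(1 − f).
- Later plateau without PE: r/(1 − r). Its ratio to P is [1 − r(1 − f)] / [(1 − r)(1 − f)].

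| f | First value / last PE-day value | Later plateau / last PE-day value, r = 0.1 to 0.5 |
|---|---|---|
| 0 | 1.0 | 1.0 |
| 0.3 | 1/0.7 = 1.43 | 1.48 to 1.86 |
| 0.5 | 1/0.5 = 2.0 | 2.11 to 3.00 |
| 0.7 | 1/0.3 = 3.33 | 3.59 to 5.67 |

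Within a phase the values do level off. With f = 0.5 and r = 0.3, PE-phase predose is 0.150 on day 2, 0.172 on day 3 and 0.176 on day 10. After PE stops it is 0.353, then 0.406, and 0.428 by the sixth day.

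**3. Make-up of the day-1 3-6 h cell**

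Inputs from the documents: PE starts 0.25 to 6 h after the bolus, and the s.c. dose follows within 0.5 h of its end. Assumed: PE duration, and uniform distributions for gap, duration, s.c. delay and sampling time (1,000,000 draws).

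| Bolus-to-PE gap | PE duration | Pre-PE | During PE | Post-PE, pre-s.c. | Post-s.c. |
|---|---|---|---|---|---|
| 0.25-6 h | 2-4 h | 26% | 51% | 4% | 19% |
| 0.25-1 h | 2-4 h | 0% | 22% | 7% | 70% |
| 0.25-1 h | 1.5-3 h | 0% | 5% | 4% | 91% |

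The cell can hold all four conditions under the permitted timing. How mixed it is in practice depends on how soon PE starts and how long it lasts. A grid enumeration with PE fixed at 2, 3 or 4 h shows the 8-24 h cell to be nearly all post-PE and post-s.c.

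**4. The overall column**

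With 1:1 arms, placebo concentrations set to zero and an ALX-0081 mean of m, the pooled mean is (m + 0)/2 = m/2.

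**The case against.** The strongest reply is that these statistics are not the whole PK analysis. Protocol 8.4.4 plans population PK modelling with covariates, and SAP 6.5.1 plans a non-linear mixed-effects PK/PD model under a separate Data Analysis Plan. That model could account for PE. This stands, so the point is confined to the descriptive summaries and the plot. However, PE is not a named covariate, the Data Analysis Plan is not among the documents, and a model does not correct a plot presented in its own right.

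A reader might infer that the plan cannot show steady state at all. The documents do not support that. The day-2 and last-PE-day predose samples are both post-PE, and the later untapered predose samples are also like for like, so a plateau can be read within each phase. The 18-24 h samples, drawn before the next PE or dose, give a further comparable series. Neither document defines which samples enter the predose plot.

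A reader might also infer that predose values will rise when PE stops. That depends on how much drug PE removes, for which no figure is given. The 1/(1 − f) step is a simplification too, because the protocol describes non-linear, target-bound kinetics (2.3.2, 2.4.1).

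Other objections narrow the point further. Several sampling-day labels already separate the phases, and tapering is not recommended (protocol 4.3). vWF and FVIII are drawn with the PK samples but summarised under SAP 6.5.2, not protocol 10.2, and the step arithmetic says nothing about them. The requirement for interpretable PK data may exclude placebo subjects in practice, and the by-treatment columns leave the ALX-0081 results visible. Even so, the text does not exclude placebo, and an overall column is informative only if both arms belong in it.

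**Conclusion.** The point holds for the descriptive outputs. As written, the plan produces a predose series whose meaning changes at the PE stop, and a day-1 3-6 h cell that need not describe one condition. Weekly predose cells are mixed wherever PE is tapered. The PK population and its overall column can also include placebo subjects.

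The size is conditional: no step if PE removes nothing, and 1.4- to 3.3-fold at the first post-PE sample for assumed removal of 30% to 70%. The day-1 split ranges from strongly mixed to about 91% in one state, depending on assumed PE timing and duration. The halved overall mean assumes equal arms and placebo values of zero.

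This is a modest weakness in a secondary, descriptive endpoint that is cheap to repair. The primary analysis and sample size are not affected.

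**What to change.** In protocol 8.4.4 and 10.2, SAP 6.5 and the Data Analysis Plan:

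- Derive a PE state for each PK sample (pre-PE, during PE, post-PE and pre-dose, or post-dose with no PE since) from recorded dose, PE and sampling times. Dose times (protocol 7.2) and PE start and end times (8.2.1.1.1) are already recorded. Confirm that the actual draw time is captured, since section 8.4.2 mentions only the scheduled time on the tube label.
- Summarise the day-1 3-6 h and weekly samples by that state.
- Define predose and plot it separately for the PE and post-PE phases. Alternatively, build the steady-state plot from the existing 18-24 h pre-PE samples and predose samples with no PE since the last dose.
- Name PE as a time-varying effect in the Data Analysis Plan.
- Flag PE state in the coupled vWF and FVIII summaries of SAP 6.5.2.
- Restrict PK concentration summaries to ALX-0081-treated subjects and drop the overall column.

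The cost is wording and programming, with no new samples or visits. The downside is fewer values per cell, mostly on day 1.

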10.3 Evaluation of Safety and Tolerability Parameters

All safety parameters (physical examination, vital signs, bleeding, ECG-parameter, biochemistry/haematology and ADA evaluations, concomitant medications (including PE characteristics) and AEs) will be summarised descriptively by treatment. Quantitative variables will be described by n, mean, standard deviation, median, minimum and maximum. Qualitative variables will be described by frequency tables containing counts and percentages. Additionally, shift tables will be provided for the safety laboratory parameters (within, below or above normal range) from pre-study to post-dose.

The AEs will be coded according to MedDRA and tabulated by system organ class, preferred term and lower level term. An AE will be referred to by the treatment and time point after which it occurred, i.e. any AE occurring before the dosing will be counted as a baseline AE and will be considered as a treatment-emergent AE only if the severity or relation to drug changes.

No formal statistical testing will be performed on the safety data.

10.4 Determination of Sample Size

For the sample size calculation SAS version 9.2 has been used.

The primary endpoint of time-to-response of blood markers (defined as time-to-response) is monitored in a survival setting.

Sample Size Calculation The time-to-response of blood markers is monitored in a survival setting. The primary endpoint time-to-response of blood markers comprises recovery of platelets $\geq 150,000/\mu\text{L}$. Accrual period is taken as 1.5 years. Zero to time-to-event period is set at 30 days. As median time-to-response for the control group we take 6 days (this information is calculated based upon Bandarenko et al.²⁸). For the treated group with ALX-0081 we assume a 44% risk reduction corresponding to a reduction in median time to event of 2.64 days, and ultimately resulting in a time-to-response of 3.36 days. The hazard ratio is defined in the SAS code as the hazard of control versus experimental (ALX-0081) treatment thus equalling to $6/3.36=1.786$. The sample size calculations are performed based on a log-rank test, aiming for a power of 80%, tested 1-sided at 2.5% significance level with 1:1 randomisation. Note that we assume that 15% of subjects would be lost-to-follow-up. The latter is justifiable because the active follow-up period only equals 30 days. Based on the above described assumptions a sample size of 110 subjects is required.

10.5 Assessment of Primary Endpoint

The primary endpoint (i.e. time-to-response of blood markers comprising recovery of platelets $\geq 150,000/\mu\text{L}$) will be formally assessed by means of a survival analysis. An SAP will be prepared before closing the database and will comprise all methods and tests applied for analysis of the data.

Assessment of the primary endpoint is performed by using a one-sided log-rank test at 2.5% significance level. A Kaplan-Meier (KM) analysis with time-to-response as the endpoint and treatment group as the independent variable, and stratified for absence/presence of one PE session prior to randomisation, will be performed on the ITT and PP populations. An observation is censored if the observation does not meet the defined time interval of 30 days after first administration of study drug medication, due to any cause of loss-to follow-up (including death), or endpoint not being reached within the defined time interval.

The log-rank test is one-sided because inhibition by ALX-0081 of vWF is expected for all subjects. Indeed, as described in section 2.4.2, 100% of subjects receiving a SD s.c. injection of 8 mg already had inhibition of RICO up to a minimum of 18 hours.

10.6 Analysis of Efficacy Parameters and Secondary Endpoints

Descriptive statistics for efficacy parameters and secondary endpoints, including PD parameters, will be presented for all available data using either the ITT population, the safety population, or the PP population. The descriptive statistics will include (but not limited to) the number of observations, mean, standard deviation, median, minimum and maximum for continuous variables and number of observations and their percentages for categorical parameters. An SAP will be prepared before closing the database and will comprise all methods and tests applied for analysis of the data.

10.7 Analysis of Tertiary and Exploratory Endpoints

[REDACTED]

11. ETHICAL ISSUES AND INSURANCE

11.1 Independent Ethics Committee

The study protocol (including all substantial amendments) together with the written informed consent form and informed consent updates, subject recruitment procedures (e.g. advertisements), any other written information to be provided to subjects, and any other documents needed by the IEC will be submitted for approval to the IEC which according to local regulatory requirements is in charge. Written approval of the study needs to be obtained from the IEC prior to the start of the study.

The Sponsor should submit written reports of the clinical study status to the IEC annually, or more frequently if requested by the IEC. A final study notification will be forwarded to the IEC within 90 days after the study has been completed or in the event of premature termination of the study within 15 days.

The IEC will be informed of all subsequent protocol amendments and of all SUSARs occurring during the study and all other events that have an impact on the safety of the subjects or the conduct of the study.

11.2 Ethical Conduct of the Study

The study will be conducted in accordance with the EU Clinical Trial Directive 2001/20/EC, the ICH guideline for GCP dated July 1996 and the ethical principles laid down in the Declaration of Helsinki (Appendix 1). Current national regulations and guidelines will also be followed.

11.3 Patient Information and Consent

The subjects or in case that the subject is physically or mentally incapable, their legal representatives according to local law will be informed about the nature and importance of the study. They will receive a detailed description of the foreseeable risks and discomforts and of the procedures to be followed. They will be informed that they are free to withdraw from the study at any time without any disadvantages. The consent form must be approved (along with the protocol) by the IEC and be acceptable to the Sponsor. The consent form must be in a language fully comprehensible to the prospective subject/representative.

In first intention, voluntary informed consent will be signed and dated by each subject and the person who conducted the informed consent discussion at screening prior to any study-

related procedures. All subjects will be fully informed about the meaning, aim and conduct of the study. This will take place under conditions where the participant has adequate time to consider the risks and benefits associated with his participation in the study. The subjects will have the possibility to ask all of their questions. By dating and signing the informed consent form, the subjects will agree to their participation in the study.

In second intention, in the expected case where subjects cannot provide informed consent due to physical or mental incapacity, a legal representative of the subject will be able to provide consent according to local requirements, and regulations and IEC approval. In the clinical setting of this trial investigating the acute phase of TTP, this occurrence is expected to be more frequent, with a more severe intensity of physical and/or mental incapacity. If local requirements, regulations and ethical committees allow, the study can be initiated prior to obtaining the informed consent, in case of physical or mental incapacity to consent and absence of a legal representative.

As soon as possible, voluntary informed consent must be sought and obtained from these physically or mentally incapacitated subject, or legal representative, as applicable.

It is the responsibility of the Investigator to assure that informed consent is obtained for each participant in accordance with Section 4.8 of the ICH consolidated guideline for GCP from July 1996, and local regulations. The signed informed consent will be retained with the study records. Each participant will receive a copy of the signed informed consent.

The Investigator should maintain a log of all subjects who sign the informed consent form and indicate if the subject received study drug or, if not, the reason why. The subject's medical records should also document that the informed consent form was signed and dated prior to any study-related procedures being performed.

